## CDI group:

- 17. The patient was treated with drugs and therapies to treat CDI within 24 hours before the start of IMP administration
- 18. The patient with severe and complex CDI who has any of the following at the screening examination.
  - Complicated disease: ileus, mental status changes, organ dysfunction (kidney and respiratory organs), septic shock, peritonitis, toxic megacolon, marked dehydration
  - Admission to intensive care unit due to CDI

## Enteric infection group:

- 19. The patient was treated with other antibacterial agent by oral administration or injection within 7 days before the start of IMP administration.
- 20. Typhoid bacillus, *Salmonella paratyphi* A, enterohemorrhagic *E. coli, Shigella*, or *V. cholerae* was isolated/identified.
- 21. The patient has marked dehydration at the screening examination.

# 6 Trial Design

# 6.1 Dose, Regimen, and Treatment Period

Start with the 100 mg group, and the safety and efficacy during the treatment period will be assessed by the DRC. If the 100 mg has no safety concerns and the efficacy is assessed "effective," 10 patients each who were not in the 100 mg group will be randomized to the 200 mg or 50 mg group, and the two groups will be treated in parallel. If the 100 mg has no safety concerns and the efficacy is assessed "not effective," 10 patients who were not in the 100 mg group will be allocated to the 200 mg group as the next step. After the assessment by the DRC based on the safety of the 200 mg group during the treatment period, start dosing for the 400 mg group. Treatment will be started in the CDI and enteric infection groups, respectively.

Table 6.1-1 shows the dosage and formulations selected for each dosing group.

- Daily dosage: OPS-2071 50 mg, 100 mg, 200 mg, 400 mg
- Number/route of administration: twice daily, morning and evening/oral administration
- Take IMP after meal where possible with at least 10 hours of interval between dosings. Ensure to have evening meal before dosing on the previous day of blood collection for PK and to have breakfast before dosing on the day to perform blood collection for PK.
- Treatment period: 10 days for CDI group and 7 days for enteric infection group

  Note: Whether or not the symptoms improve during the treatment period, use
  all IMPs prescribed for the predetermined period.

Table 6.1-1 Dosage and Formulations for Each Dosing Group

Dosing Group	Dosage of OPS-2071	Formulation			
50 mg group	50 mg/day	25 mg tablet $\times$ 1, twice daily			
100 mg group	100 mg/day	50 mg tablet × 1, twice daily			
200 mg group	200 mg/day	100 mg tablet × 1, twice daily			
400 mg group	400 mg/day	100 mg tablet × 2, twice daily			

### [Rationale for dose and regimen]

It has been confirmed that there are no safety concerns up to 1200 mg in the phase 1 single dose study in healthy male adults and up to 1200 mg per day in the 7-day multiple dose study (twice daily after meals). The barrier function of membranes may be deteriorated because of infection in patients with enteritis, which may increase the absorption of the drug. OPS-2071, with favorable membrane permeability, is unlikely to

increase absorption in patients with enteritis relative to healthy adults.

In a non-clinical pharmacological study, therapeutic effect of OPS-2071, VCM, and FDX was assessed using the hamster CDAD model. Significant therapeutic effect was demonstrated by OPS-2071 at 0.04 to 1 mg/kg, and VCM and FDX at 1 to 5 mg/kg, showing that OPS-2071 has therapeutic effect comparable with or higher than FDX and VCM at doses 1/5 to 1/25 times lower than FDX and VCM. According to the calculation of clinical dose, 16 to 100 mg of OPS-2071 is expected to have therapeutic effect comparable to or higher than VCM (clinical dose 500 mg) and FDX (clinical dose 400 mg).

Based on the above, 100 mg/day, the clinically recommended dose at present from which the efficacy can be certainly expected among clinical dose ranging 16 to 100 mg/day is selected for the starting dose. If there are no safety concerns and the efficacy is confirmed in the 100 mg group, the safety and efficacy of OPS-2071 will be assessed at 50 mg/day, the low dose cohort, and at 200 mg/day, 2-fold higher than the clinically recommended dose. If the efficacy at 100 mg/day is not confirmed and there are no safety concerns, the safety and efficacy of OPS-2071 will be assessed at up to 400 mg/day in a sequential ascending manner. Thus, the trial has a dose increase/decrease design.

This trial is designed for twice-daily administration of OPS-2071, the same as in the phase 1 multiple-dose trial, with an interval of at least 10 hours between dosings.

It is demonstrated that OPS-2071  $C_{max}$  is higher by 2.21 times and  $AUC_{0-t}$  by 2.04 times in administration after taking high fat meal relative to fasting. Administration after meal is desirable for the assessment of safety and PK at higher exposure. On the other hand, patients with severe symptoms of bacterial enteritis may not be able to take meals. Thus, the IMP should be administered after a meal where possible. However, for PK assessment in a steady state, the IMP must be administered after dinner on the day before blood sampling and after breakfast on the day of blood sampling to avoid any influence on PK assessment.

#### 6.2 Prior and Concomitant Treatment

If a drug other than an IMP has been used during the period from the acquisition of consent to the end of the trial, the name of the drug, purpose of use, mode of administration, daily dose, route of administration, and dates of start and end of administration will be recorded in the source documents and case report form (CRF). For

a non-drug therapy, the name of therapy, purpose, and dates of start and end of that therapy treatment will be recorded in the source documents and CRF. For CDI group, if a drug or therapy from either item 7 in the list of prohibited concomitant drugs and therapies or item 1 in the list of restricted concomitant drugs and foods has been used during the period from 7 days before the start of IMP administration to the start day of the IMP administration, such will also be recorded in the source documents and CRF.

To avoid emergent risks such as the need for treatment of an AE, if it is necessary to treat a patient with a prohibited concomitant drug or therapy, the patient will be withdrawn from this trial according to Section 9.2, Criteria and Procedures for Withdrawal of Individual Patients.

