# 3.3.2 Efficacy Endpoints

# 3.3.2.1 Microbiological Outcome

Microbiological outcome will be judged according to the assessment criteria shown in Table 3.3-1 and Table 3.3-2 for the bacterial strain isolated as the causative pathogen based on the data from the microbiological examination. For infection due to multiple causative pathogens, microbiological outcome will be assessed for each individual pathogen.

 Table 3.3-1
 Assessment Table for Microbiological Outcome

	Assessment of				
Baseline	Day 4	End of Treatment	Microbiological Outcome		
+	-	_	Excellent		
+	1				
_	+	_	Good		
+	Not applicable				
+	1				
_	+	,	Poor		
+	_	+			
+	Not applicable				
	Others		Unknown/ indeterminate		

+: culture positive, -: culture negative

Not applicable: Bacterial culture test was not performed. The causative pathogen was not isolated or identified.

Table 3.3-2 Assessment Criteria for Microbiological Outcome

Assessment of Microbiological Outcome	Definition			
Excellent	Pathogen is absent from bacterial culture obtained at Day 4 and at the end of treatment.			
Good	Pathogen is still present in bacterial culture obtained at Day 4, and absent from bacterial culture at the end of treatment.			
Poor	Pathogen is still present in bacterial culture obtained at the end of treatment.			
Unknown/indeterminate	Applicable to none of the above but falls under the cases below for example.     Cultures are not available because of withdrawal from the study or other reasons.			
	Culture was obtained after the use of prohibited concomitant drugs/therapies.			
	Any other circumstance, which makes it impossible to define the microbiological response.			

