# 3.3.2.3 Clinical Response

The investigator or subinvestigator will refer to the information from patients (eg, patient diary), and assess clinical response at the time of observation (Day 4 and end of treatment) according to the assessment criteria shown in Table 3.3-3.

Table 3.3-3 Assessment Criteria for Clinical Response

Clinical Response Assessment	Definition
Clinical cure	Meeting all the following criteria within 24 hours before observation  No liquid or unformed stool
	No abdominal symptoms and no other symptoms (fever, nausea, vomiting)
	No need of medication or therapy to treat CDI or enteric infection
Clinical improvement	Fulfilling at least one of the following criteria within 24 hours before observation  • Liquid or unformed stools ≤ 2 times/day
	No abdominal symptoms and no other symptoms (fever, nausea, vomiting)
	No need of medication or therapy to treat CDI or enteric infection
Clinical failure	Fulfilling none of the above-mentioned clinical improvement criteria.  Patients who received medication or therapy to treat CDI or enteric infection prior to the time of observation are to be assessed as "clinical failure".

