## 6.2.1 Prohibited Concomitant Drugs and Therapies

The use of following drugs and therapies will be prohibited during the period from the start day of IMP administration to the end day of the trial for items 1 and 7, from screening to the end day of the trial for the following items 2 through 6, and from the start day of IMP administration to the end day of IMP administration for item 8.

- 1) For enteric infection group only: antibiotic agents/synthetic antibacterial agents (oral, injection, suppository)
- 2) For enteric infection group only: non-steroidal anti-inflammatory/analgesic drugs (oral, injection, suppository)\*
- 3) For enteric infection group only: corticosteroid preparation (oral, injection, suppository)
- 4) For enteric infection group only: immunosuppressant medications (oral, injection, suppository)
- 5) For enteric infection group only: biological preparation (TNF inhibitor)
- 6) Antidiarrheal drugs, drugs to inhibit bowel motility
- 7) Other drugs and therapies to treat CDI and enteric infection (eg, fecal microbiota transplantation)
- 8) UGT1A1 inhibitors (atazanavir)
  - \*: Use for purposes other than treating enteric infection is allowed. (Concomitant use is allowed for treating common cold during the trial period.)

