#### 9.2 Criteria and Procedures for Withdrawal of Individual Patients

In any of the events listed below, the investigator or subinvestigator will discontinue IMP administration, perform the tests to be performed at withdrawal stipulated in Section 7.1, Schedule and Procedures of the Trial, and promptly inform the sponsor of the withdrawal (Annex, Emergency Contact). The investigator or subinvestigator will record the date and reason for withdrawal in the source documents and CRF.

If withdrawal is necessitated by problems with safety, such as the occurrence of an AE or aggravation of the underlying disease, the investigator or subinvestigator will promptly take appropriate measures and perform follow-up if necessary (refer to Section 8.4 Follow-up Investigation of Adverse Events).

- 1. If the patient wishes to withdraw
- 2. If it is found after the start of the trial that the patient did not meet all the inclusion criteria or fell under any of the exclusion criteria
- 3. If a drug or therapy from either item 1 or item 7 in the list of prohibited concomitant drugs and therapies is used or judged to be required
- 4. If an AE making continuation of trial participation difficult occurs
- 5. If the female patient is found to be pregnant
- 6. If symptoms of the primary disease exacerbate, and the investigator or subinvestigator judges that it is not appropriate to continue the trial participation
- 7. If it becomes impossible to comply with the protocol for any another reason or if the investigator or subinvestigator judges that it is necessary to discontinue the trial participation for any another reason

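### Sections 6.2 and 9.2 disagree on which prohibited drugs lead to withdrawal, and neither clinical cure nor time to resolution of diarrhea has a rule for antidiarrheal use

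*Protocol*

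**What the plan says.** **Withdrawal.** Section 6.2 states: "if it is necessary to treat a patient with a prohibited concomitant drug or therapy, the patient will be withdrawn from this trial", and the same sentence names the section that governs this: "the patient will be withdrawn from this trial according to Section 9.2". It does not restrict this to particular items of the prohibited list. Criterion 3 of Section 9.2 begins: "If a drug or therapy from either item 1 or item 7 in the list of prohibited concomitant drugs and therapies is used", and also covers the case where such a drug is judged to be required. The synopsis repeats it. No criterion names items 2 to 6 or 8. The nearest is criterion 7, "If it becomes impossible to comply with the protocol for any another reason", which also allows withdrawal at the investigator's judgement.

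**Antidiarrheals.** Item 6 of Section 6.2.1 is "Antidiarrheal drugs, drugs to inhibit bowel motility". It applies to both disease groups and is prohibited "from screening to the end day of the trial for the following items 2 through 6".

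**Clinical endpoints.** Table 3.3-3 assigns clinical failure to "Patients who received medication or therapy to treat CDI or enteric infection" before the observation. It does not mention prohibited drugs as a class. Section 11.1.4 defines the clinical per protocol set (CPPS) by whether scheduled examinations were done, with no exclusion for prohibited drugs. Sections 3.3.2.5, 7.2.2.5 and 11.3.4.5 take time to resolution as the time to the first formed stool, with an exception only when loose stools come back.

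**Microbiological endpoint.** Table 3.3-2 gives as one example of an unknown or indeterminate outcome: "Culture was obtained after the use of prohibited concomitant drugs/therapies".

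**The concern.** Section 6.2 makes withdrawal mandatory for any prohibited drug that is needed. The section it cites makes withdrawal specific to two of the eight items. A site working from 6.2 and a site working from 9.2 could handle the same antidiarrheal user differently, in a trial run in three countries.

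The endpoint gap is separate. Antidiarrheals act on stool count and stool form. These enter clinical cure, which decides who is assessed for CDI recurrence, and they define time to resolution. Section 6.2.2 explains that the prohibited list was drawn up partly to protect the efficacy assessment, yet the clinical endpoint definitions do not carry that through for item 6. Stools firmed or stopped by another drug could be credited to OPS-2071.

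**Working it through.** The plan states no figure on this point, so there is none to reproduce. The check is a side-by-side reading followed by the arithmetic of one patient.

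**1. Withdrawal, item by item**

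| Prohibited items | Section 6.2 | Section 9.2, criterion 3 | Other route in 9.2 |
|---|---|---|---|
| 1 and 7 | withdraw if needed | withdraw if used or needed | not required |
| 2 to 6 and 8 | withdraw if needed | not named | criterion 7, discretionary |

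Items 1 to 5 apply only to the enteric infection group. In the CDI group the prohibited items are therefore 6, 7 and 8, and criterion 3 reaches only item 7. The triggers also differ: 6.2 speaks of need, criterion 3 of use or need. A patient who took an item 6 drug unprompted falls under neither rule as written, only under criterion 7.

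**2. Clinical response for an item 6 user.** Everything turns on whether the drug counts as treatment of the infection.

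- *Reading A, it does not.* The failure rule is not triggered. Improvement needs only one of three criteria, one of which is that no treatment of the infection is needed. A patient not needing such treatment is already at least improved, whatever the stool count. Masked stools can then lift that patient from improvement to cure, provided abdominal symptoms, fever, nausea and vomiting are also absent. A patient who passes no stool also meets the stool criterion for cure.
- *Reading B, it does.* The patient is a clinical failure.

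Within reading A, masking adds up to one cure per patient and no responder to the pooled cure-plus-improvement rate. Within reading B it adds neither. The pooled rate differs by one patient only between the two readings, which is a matter of classification.

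**3. Cure rate.** Input: 10 patients per dose and disease group (Section 3.4). Change per patient = 1/10 = 10 percentage points. With assumed counts and Clopper-Pearson intervals:

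- 7/10 = 70% (95% CI 34.8% to 93.3%)
- 8/10 = 80% (95% CI 44.4% to 97.5%)

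The shift is small against the width of either interval.

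**4. Recurrence (CDI group only).** The denominator is patients with clinical cure at the end of treatment (Sections 3.3.2.4 and 11.3.4.4). With 7 true cures and 1 recurrence, both assumed, the rate is 1/7 = 14.3%. One added masked cure gives 1/8 = 12.5% if that patient does not recur, or 2/8 = 25.0% if the patient does. The direction is not fixed.

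**5. Time to resolution.** If the drug brings one patient's first formed stool forward by *d* days, the mean over 10 patients falls by *d*/10. The documents give no value for *d*. The exception for returning loose stools protects only when they come back. This endpoint has no failure rule, so the gap exists under both readings.

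**6. Would withdrawal close the gap?** No. Sections 7.1.7.1 and 7.1.7.2 require clinical response to be assessed at withdrawal during treatment, and the CPPS accepts examinations up to withdrawal.

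**The case against.** **Criterion 7 already covers the other items.** It gives a route, but a discretionary one, where 6.2 is mandatory. Naming items 1 and 7 in criterion 3 would also serve little purpose if criterion 7 were meant to cover every item. The mismatch stands.

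**An antidiarrheal given for the enteritis is already a failure.** Item 7 opens with the word *Other*, which can imply that the preceding items count as treatment of the infection when used for it. Purpose of use is recorded for every drug, so an investigator could reasonably apply this. This much stands: the reading is open. But the protocol does not state it, criterion 3 treats item 7 apart from item 6, and time to resolution has no such rule on either reading.

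**The response rate does not move.** A reader might infer that 1 or 2 users in a cell of 10 would inflate the clinical response rate by 10 to 20 points. The documents do not support that, because improvement needs only one criterion (working, step 2). The exposure lies in the cure category.

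**Microbiological exclusion is not established.** A reader might also infer that the same patient is bound to drop out of the elimination rate. Table 3.3-2 reserves the unknown category for cases that fit none of the other grades, and Table 3.3-1 grades on culture results alone. A patient with gradable cultures is not clearly excluded.

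**Derivation rules belong in the SAP.** This is partly right. Section 11 defers details to the SAP, which is not at hand, and Section 11.2 lets the sponsor decide on problematic data. A rule for time to resolution, which the sponsor derives, could sit there. Clinical response is graded by the investigator from Table 3.3-3, so its rule has to be in the protocol, as does the wording of 6.2 and 9.2.

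**Conclusion.** The point holds in two separate parts. First, Section 6.2 contradicts Section 9.2 and the synopsis on whether items 2 to 6 and 8 require withdrawal. This rests on the text alone. Second, an item 6 user can be scored as clinically cured, enter the recurrence denominator and be given an early first formed stool because of that drug. For cure and recurrence this depends on the investigator not reading item 6 as treatment of the infection; for time to resolution it does not.

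Each affected patient moves the cure rate in a cell of 10 by 10 points. The protocol gives no frequency of such use, so the total effect cannot be estimated. A shift in the pooled response rate and a certain exclusion from the microbiological analysis are not shown. In a descriptive phase 2a trial with no hypothesis test, this is a correction that should be made, not a flaw that invalidates the design.

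**What to change.** 1. Reconcile Section 6.2, Section 9.2 and the synopsis so that one list governs withdrawal and the trigger (use, need or both) is the same throughout. Which items belong on it is the sponsor's clinical decision.
2. In Table 3.3-3 and its copy in the synopsis, state that a patient who used an item 6 drug before the observation is not counted as clinical cure at that visit, and state how such use is treated for clinical improvement. This also settles entry to the recurrence denominator.
3. In Section 11.3.4.5, and in the definitions in 3.3.2.5 and 7.2.2.5, state that a formed stool after first use of an item 6 drug is not credited as resolution.
4. Align these rules with the prohibited-drug wording of Table 3.3-2, and make clear whether that wording overrides a gradable culture.

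The cost is protocol wording and one derivation rule. Section 6.2 already has drug name, purpose and dates recorded, so no new data are needed. Cure rates may come out slightly lower and times to resolution slightly longer.

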## 6.2.1 Prohibited Concomitant Drugs and Therapies

The use of following drugs and therapies will be prohibited during the period from the start day of IMP administration to the end day of the trial for items 1 and 7, from screening to the end day of the trial for the following items 2 through 6, and from the start day of IMP administration to the end day of IMP administration for item 8.

- 1) For enteric infection group only: antibiotic agents/synthetic antibacterial agents (oral, injection, suppository)
- 2) For enteric infection group only: non-steroidal anti-inflammatory/analgesic drugs (oral, injection, suppository)\*
- 3) For enteric infection group only: corticosteroid preparation (oral, injection, suppository)
- 4) For enteric infection group only: immunosuppressant medications (oral, injection, suppository)
- 5) For enteric infection group only: biological preparation (TNF inhibitor)
- 6) Antidiarrheal drugs, drugs to inhibit bowel motility
- 7) Other drugs and therapies to treat CDI and enteric infection (eg, fecal microbiota transplantation)
- 8) UGT1A1 inhibitors (atazanavir)
  - \*: Use for purposes other than treating enteric infection is allowed. (Concomitant use is allowed for treating common cold during the trial period.)

# 6.2.2 Restricted Concomitant Drugs and Foods

Restricted concomitant drugs and foods among of drugs listed below, concomitant use of drugs listed in 1) in principle are prohibited from the start day of the IMP administration to the day of examination at the end of treatment if the drug is used for a purpose other than treatment of CDI.

Protocol No. 341-13-002

However, in cases that drugs are used to treat an underlying disease at the time of screening and cannot be discontinued even after the start day of the IMP administration due to the necessity for continuous drug treatment, such concomitant use is allowed. Drugs listed in items 2) through 5) are allowed to be administered concomitantly as long as the drugs are used at the time of screening and the dose regimen is not changed during the period from screening until the day of examination at the end of treatment.

Drugs listed in item 6) are allowed to administer concomitantly under the following condition: the drugs are used at the time of screening, and the dose regimen is not changed in the period from screening to the end day of trial for CDI groups, or the period from screening to the end day of IMP administration for enteric infection group. If the food described in item 6) is taken, instruct the patient not to change the daily amount of consumption in the period from screening to the end day of the trial.

- 1) For CDI group only: antibiotic agents/synthetic antibacterial agents (oral, injection, suppository)
- 2) For CDI group only: non-steroidal anti-inflammatory/analgesic drugs (oral, injection, suppository)\*
- 3) For CDI group only: corticosteroid preparation (oral, injection, suppository)
- 4) For CDI group only: immunosuppressant medications (oral, injection, suppository)
- 5) For CDI group only: Biological preparation (TNF inhibitor)
- 6) Probiotics
- \*: Use for purposes other than treating CDI is allowed. (Concomitant use is allowed for treating common cold during the trial period.)

[Rationale for establishing the prohibited and restricted concomitant drugs and therapies]

The above defined prohibited and restricted concomitant drugs and therapies were set considering the possible impact on the proper assessment of the efficacy and safety of IMPs. Topical use is allowed for 1) to 4) of the prohibited concomitant drugs.

Since OPS-2071 is metabolized by UGT1A1 and UGT1A9, concomitant use of No. 8) in the list of prohibited concomitant drugs may increase the plasma concentration of OPS-2071. To secure safety, concomitant use of inhibitors that may increase plasma concentrations of OPS-2071 is prohibited.

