#### 1 Introduction

# 1.1 Background of Trial Plan

According to the World Health Organization (WHO) report, diarrheal disease is in the top-10 list of leading causes of death in the world, with 1.5 million people dying from diarrheal disease in 2012.  Diarrhea is the major symptom of enteric infections caused by bacteria such as *Salmonella*, *Campylobacter*, *Vibrio*, *Shigella*, and *Escherichia coli* (*E. coli*). In addition, a number of antibiotic-resistant pathogens have been reported in recent years,  and quinolone-resistant *Campylobacter* in particular has become widespread. 

All of the commercially available antibiotics have the potential to cause diarrhea during treatment of infectious diseases. Use of antibiotics sometimes disrupts intestinal flora, followed by microbial substitution, which leads to an increase in pathogenic bacteria and eventually induces diarrhea (antibiotic-associated diarrhea: AAD). Since *Clostridium difficile* (*C. difficile*) is resistant to most of the currently available antibiotics, and AAD caused by *C. difficile* is specifically known as *C. difficile* infection (CDI). Use of existing quinolone drugs has been known to increase the risk of CDI, and the number of CDI cases has been increasing in recent years. Metronidazole (MTZ) and vancomycin (VCM) are the preferred first-line therapeutic agents for CDI; however, treatment failure with the use of MTZ and recurrence with the use of VCM in 15% to 30% of cases have been reported. An additional concern regarding the use of VCM is the emergence of VCM-resistant enterococci (VRE).

In order to solve these problems, Otsuka Pharmaceutical Co. Ltd. discovered OPS-2071, which shows a broad spectrum of activity against intestinal infectious bacteria, including *C. difficile* and *Campylobacter*, and is expected to cause few adverse effects because of its low systemic absorption following oral administration. OPS-2071 is a new chemical entity with a quinolone structure for enteric infections, including CDI.

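### In the CDI group, a negative culture or clinical response under a permitted C. difficile-active antibacterial can be credited to OPS-2071, because no explicit outcome rule covers it

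*Protocol*

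**What the plan says.** **Concomitant drugs, CDI group.** Section 6.2.2, item 1 of the restricted list, reads "For CDI group only: antibiotic agents/synthetic antibacterial agents (oral, injection, suppository"). These drugs are barred in principle from the first dosing day to the end-of-treatment examination "if the drug is used for a purpose other than treatment of CDI". An exception follows for a drug already in use at screening for an underlying disease that has to go on: "due to the necessity for continuous drug treatment, such concomitant use is allowed". The exception sets no condition on agent or spectrum.

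**Prohibited list.** Section 6.2.1 items 1 to 5 apply to the enteric infection group only. For CDI patients that leaves item 6 (antidiarrheals and motility inhibitors), item 7 ("Other drugs and therapies to treat CDI and enteric infection (eg, fecal microbiota transplantation")) and item 8 (UGT1A1 inhibitors).

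**Entry.** Exclusion 17 in Section 5.3 reads: "The patient was treated with drugs and therapies to treat CDI within 24 hours before the start of IMP administration".

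**Outcome rules.** Table 3.3-2, repeated in the Synopsis, gives examples of an unknown/indeterminate microbiological outcome. The only drug-related one is: "Culture was obtained after the use of prohibited concomitant drugs/therapies". The list ends with an open category for any other circumstance that prevents a judgement. In Table 3.3-3 the medication criterion for cure and improvement is "No need of medication or therapy to treat CDI or enteric infection", and only patients who received such treatment are set to clinical failure.

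**Analysis sets.** The MPPS (Section 11.1.3) drops only unknown/indeterminate outcomes. The CPPS (Section 11.1.4) requires only that scheduled examinations were done. Neither mentions concomitant antibacterials.

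**Agents named in the protocol.** Section 1.1 states: "Metronidazole (MTZ) and vancomycin (VCM) are the preferred first-line therapeutic agents for CDI". Section 1.2.1.1 describes rifaximin as comparable to OPS-2071 in activity against C. difficile in vitro.

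**The concern.** The restricted list sorts antibacterials by why they are given. The efficacy question depends on what they do to the causative pathogen. The outcome rules follow the list rather than the question, so a co-administered drug that could itself clear C. difficile need not affect how the culture or the clinical response is scored.

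The trial has no comparator arm and plans 10 CDI patients per dose, so the effect of such a drug cannot be separated from that of OPS-2071. Elimination rate, clinical response and toxin result are all exposed. Recurrence is exposed too, because the item 1 restriction ends at the end-of-treatment examination while recurrence is judged up to Day 38. The 100 mg efficacy judgement also decides whether the trial goes on to 50 and 200 mg or to 200 and 400 mg (Section 3.1), so a misattributed success could feed into the dose path.

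**Working it through.** **1. Trace one patient through the rules.** Take a CDI patient on an exempt systemic antibacterial with C. difficile activity, whose cultures are positive at baseline and negative on Day 4 and at end of treatment.

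- Section 6.2.2: use is permitted.
- Table 3.3-1: positive, negative, negative is Excellent.
- Table 3.3-2: the drug is restricted, not prohibited, so the drug-related example of an indeterminate outcome is not met.
- Section 11.1.3: the patient is in the MPPS.
- Section 11.3.4.1: the strain counts in the numerator of the elimination rate.
- Table 3.3-3: the drug is not given to treat CDI, so the failure rule is not triggered and the response criteria can be met.

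**2. Compare the enteric infection group.** There the same drug class is prohibited to the end of the trial (Section 6.2.1 item 1). Its use meets the drug-related example in Table 3.3-2 and is a withdrawal criterion (Section 9.2 item 3). For CDI the class sits on the other list, but the voiding rule refers only to the prohibited one.

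**3. Purpose or drug class.** Section 6.2.2 item 1 is worded by purpose. Item 7 and exclusion 17 speak of drugs to treat CDI and can be read either way. Read by class, they would catch metronidazole or vancomycin given for something else. Read by purpose, they would not. Section 6.2 lists item 7 and restricted item 1 separately for recording but does not settle the question.

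**4. Size.** The planned numbers reproduce: 3 doses × (10 + 10) = 60. Section 11.5 assumes detection of about 100% in CDI and 50% in enteric infection, so 10 × 1.00 = 10 assessable CDI patients and 10 × 0.50 = 5 assessable enteric patients per dose.

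Let r be the true success rate and k the number of exposed patients among 10, all scored as successes. The protocol gives neither, so both are assumptions.

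Expected observed rate = [r(10 − k) + k]/10, and inflation = k(1 − r)/10.

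| r | k = 1 | k = 2 | k = 3 |
|---|---|---|---|
| 50% | 55% (+5) | 60% (+10) | 65% (+15) |
| 70% | 73% (+3) | 76% (+6) | 79% (+9) |
| 80% | 82% (+2) | 84% (+4) | 86% (+6) |

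**5. Effect of recoding one patient, starting from 7/10** (Clopper-Pearson 95% intervals):

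- As observed: 7/10 = 70% (34.8 to 93.3).
- One exposed success made indeterminate: 6/9 = 66.7% (29.9 to 92.5), a drop of about 3 points.
- One exposed failure made indeterminate: 7/9 = 77.8% (40.0 to 97.2), a rise of about 8 points.
- For comparison, one success counted as failure: 6/10 = 60% (26.2 to 87.8), a drop of 10 points. This coding is not proposed.

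**The case against.** **Cultures are not voided for prohibited drugs alone.** The indeterminate cases are examples, and the last is an open category. Section 11.2 also lets the sponsor, with expert advice, decide how to handle a problematic patient or data. This stands against any claim that nothing could exclude such a patient. It does not close the gap. The open category names no antibacterial, is applied by the sponsor in an open-label trial (Section 7.2.2.1), and has no counterpart for clinical response or recurrence. Section 11.2 sets no rule.

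**Metronidazole and vancomycin may be caught elsewhere.** A reader might infer that a patient kept on metronidazole for another disease certainly counts as a success. The documents do not support that. Item 7, exclusion 17 and withdrawal criterion 3 may apply by class, and exclusions 2 and 16 leave further discretion. The patient must also still turn culture-negative or meet the response criteria.

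**Exposure may be uncommon.** The exception covers only a drug in use at screening that cannot be stopped. Entry requires at least 3 loose stools in 24 hours and a positive CDI finding within 48 hours before dosing, so the disease is active despite the co-drug. Section 1.1 says C. difficile resists most available antibiotics. All this makes the case less frequent. It does not remove it, since a co-drug may have been started shortly before screening.

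**Exposure will be visible.** Section 6.2 records drug name, purpose, dose and dates, and Section 11.3.2 tabulates concomitant drugs by disease group and dose. A sensitivity analysis could also sit in an SAP that is not shown. That is fair for the sensitivity analysis. The classification rule, however, is fixed in the protocol's outcome tables.

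**Conclusion.** The point holds as a gap in the outcome rules. The protocol permits a C. difficile-active antibacterial in some CDI patients, has no explicit rule for scoring cultures, clinical response or recurrence under it, and leaves unclear whether purpose or class governs item 7 and exclusion 17. The CDI rates can therefore include successes that are not attributable to OPS-2071.

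The effect per patient is modest: about 3 points when one success in 7/10 becomes indeterminate, well inside the 34.8 to 93.3% interval. The 2 to 15 point inflation in the table rests on an assumed 1 to 3 exposed patients per 10, all scored as successes, and on assumed true rates of 50 to 80%. The protocol gives no exposure frequency.

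Two further inferences are not supported. One is that each exposed patient moves the rate by 10 points, which is true only if a success is recoded as a failure. The other is that non-CDI antibacterials after Day 11 must lower recurrence. Section 1.1 says antibiotics can disrupt the flora and induce diarrhea, so the direction is open.

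**What to change.** Change outcome coding only and leave permitted treatment as it is.

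1. **Reconcile** Sections 3.3.2.1, 3.3.2.3, 5.3 (exclusion 17), 6.2.1 (item 7) and 6.2.2 (item 1), and state whether purpose or drug class governs. No view is taken here on which it should be.
2. **Extend Table 3.3-2 and its copy in the Synopsis.** Keep the existing drug-related case and add another: a culture obtained during or after concomitant use of a systemic antibacterial on a pre-specified list of agents active against the causative pathogen, whatever the indication, is unknown/indeterminate. Apply it to positive and negative cultures alike, as the existing rule does, so that the coding does not favour either result.
3. **Present** elimination, clinical response, toxin and recurrence rates with and without patients exposed to a listed agent between first dose and the assessment.

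**Cost.** A drug list drawn up in advance and a few lines of table and analysis text. The drug data are already collected under Section 6.2. The assessable CDI denominator may shrink slightly (7/10 may become 6/9). Because Sections 3.4 and 11.5 call for additional enrolment when too few patients are assessable, a patient who becomes indeterminate may trigger a replacement.
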